## 17.4 Safety Analyses

The safety and tolerability of opaganib will be determined by reported AEs, physical examinations, vital signs, and laboratory tests. Patients who receive at least one dose of study drug are considered evaluable for safety (Safety analysis set). Detailed specification of the safety analyses will be provided in the SAP.

# **Version Control Page**

Version:	Version Date:	Comments
1	12-MAY-2020	Initial version
2	16-JULY-2020	Amendment following FDA recommendations
3	25 -Oct-2020	Amendment following sponsor request for subgroup additions
4	13-DEC-2020	Final clarification prior to unblinding for primary outcomes results (early unblinding)

# LIST OF ABBREVIATIONS AND DEFINITIONS OF TERMS

AE	Adverse Event
ВМІ	Body Mass Index
ATC	Anatomical Therapeutic Chemical
AUC	Area Under the Curve
DB	Double Blind
DM	Data Management
HFNC	High flow nasal canula
ITT	Intention to Treat
MedDRA	Medical Dictionary for Regulatory Activities
mITT	Modified Intention to Treat
PEEP	Positive End Expiratory Pressure
РТ	Preferred Term
SAE	Serious Adverse Event
SAP	Statistical Analysis Plan
SD	Standard Deviation
SE	Standard Error
TEAE	Treatment Emergent Adverse Event
TESAE	Serious Treatment Emergent Adverse Event

#### **1 PREFACE**

This Statistical Analysis Plan (SAP) describes the planned analysis and reporting for RedHill Biopharma Ltd. study ABC-110 (Opaganib, a Sphingosine Kinase-2 (SK2) Inhibitor in COVID-19 Pneumonia: a Randomized, Double-blind, Placebo-Controlled Phase 2a Study, in Adult Subjects Hospitalized with SARS-CoV-2 Positive Pneumonia), and was written in accordance with SOP 100-60-02 (Statistical Analysis Plan Preparation, Review and Approval, Bioforum's Procedure).

The structure and content of this SAP provides sufficient detail to meet the requirements identified by the FDA and International Conference on Harmonization of Technical Requirements for Registration of Pharmaceuticals for Human Use (ICH): E9 Guidance on Statistical Principles in Clinical Trials. All work planned and reported for this SAP will follow internationally accepted guidelines, published by the American Statistical Association, and the Royal Statistical Society, for statistical practice.

The following documents were reviewed in preparation of this SAP:

- Clinical Study Protocol ABC-110, version 1.2,30 August 2020.
- Case report forms (CRFs) for Study ABC-110.
- ICH E9 Guidance on Statistical Principles for Clinical Trials.
- ICH E3 Structure and Content of Clinical Study Reports
- COVID-19: Developing Drugs and Biological Products for Treatment or Prevention Guidance for Industry, May 2020.
- Statistical Considerations for Clinical Trials During the COVID-19 Public Health Emergency, Guidance for Industry, June 2020

The reader of this SAP is encouraged to also read the clinical protocol for details on the conduct of this study, and the operational aspects of clinical assessments and timing for completing a patient in this study. When differences exist in descriptions or explanations provided in the protocol and this SAP, the SAP prevails. Any deviations from the statistical analyses planned in the protocol will be documented in the SAP and any deviations from the statistical analyses planned in the SAP will be documented in the final clinical study report (CSR).

Version 1 of the SAP describes the statistical analyses as foreseen at the time of planning the study and version 2 incorporates an amendment responding to FDA recommendations received prior to study initiation, including additional clarifications and edits made early during initiation of study. Version 3 of the SAP include final clarifications and updates based on blinded data review and is finalized before the first database lock and before breaking the blind of the study. Any changes made after this event will be documented in the final CSR. First database lock refers to the event of locking all data up to and including Day 14 visit, enabling the final analysis of the Primary endpoint and those Secondary endpoints with timeframe of 14 days.

### **2 STUDY OBJECTIVES**

### 2.1 Primary

To evaluate the total oxygen requirement (area under the curve) using daily supplemental oxygen flow (L/min) over 14 days (Day 1 to Day 14)

### 2.2 Secondary

1. To evaluate the time to 50% reduction from baseline in supplemental oxygen based

on oxygen flow in L/min

- To evaluate the proportion of patients no longer requiring supplemental oxygen for at least 24 hours by Day 14
- 3. To evaluate the proportion of afebrile patients at Day 14
- 4. To evaluate the time to negative swabs for SARS-CoV-2 by PCR
- To evaluate the proportion of patients with negative swabs for SARS-CoV-2 by PCR at Day 14
- 6. To evaluate the need for intubation and mechanical ventilation by Day 14
- 7. To evaluate the time to mechanical ventilation
- 8. To evaluate the proportion of patients, with at least one measurement of fever at baseline (defined as temperature >38.0 C[100.4 F]), who are afebrile (defined as temperature <37.2C [99 F]) at Day 14
- 9. To evaluate mortality 30 days post-baseline

# 2.3 Exploratory

To assess the change in systemic markers of inflammation (D-dimer, cardiac troponin, C-reactive protein [CRP], lactate dehydrogenase [LDH] and ferritin)

# 2.4 Safety

To assess the safety and tolerability of opaganib administered orally at 500 mg Q 12 hours, for up to 2 weeks, in patients with COVID-19 pneumonia.

#### **3 STUDY DESIGN**

### 3.1 General Design and Study Schema

This is a phase 2a, proof of concept, multi-center randomized double-blind, parallel arm, placebo controlled study.

After informed consent is obtained, patients will enter a screening phase for no more than 3 days, to determine eligibility.

[figure not shown]
Approximately 40 eligible patients will be randomized to receive either opaganib added to standard of care, or matching placebo added to standard of care, in a randomization ratio of 1:1. Patients will be stratified based on a minimization algorithm, as specified in section 3.4. Treatment assignments will remain blinded to the patient, investigator and hospital staff, as well as the sponsor. As there is currently no consensus for a definitive treatment specifically targeting the SARS-CoV-2 virus causing COVID-19 (K. Wilson, 2020), standard of care will refer to regional, institutional or physician directed therapies, that may be implemented during the COVID-19 pandemic.

Study participants will receive either opaganib 2 x 250 mg capsules (500 mg) every 12 hours, or matching placebo, in addition to standard of care (pharmacological and/or supportive). Study drug will be administered every day for 14 days (Day 1 to Day 14), unless the patient has been discharged from the hospital without requiring supplemental oxygen, in which case study drug will only be administered to Day 10.

All participants will be followed up for 4 weeks after their last dose of study drug, which may occur at the end of the 2-week double-blind treatment phase or after premature study drug discontinuation, based upon patient or physician determination.

The maximum duration of study participation will be 45 days (including up to 3 days screening; 2 weeks double-blind (DB) phase and 4-weeks off-study drug follow-up).

The study schema is presented below and Visit-specific procedures and assessments are outlined in Table 1.

Off-study drug follow-up starts when study drug is stopped per protocol or after discontinuation per patient or physician decision

Assessments	Screening	Randomizatio n	DB	Phase	Early termination	Safety follow-up
	Days -3 - 1	Day 1	Day 7	Day 14	termination	ionow up
ICF signed	X					
Inclusion/exclu sion criteria	X					
Demographics; medical and surgical history	X					
Review concomitant medication(s) 	X	X	X	X	X	X
Review of adverse events 		X	X	X	X	X
Physical examination 	X		X	X	X	X
Vital signs 	X	X	Χ	X	X	X
Oxygen flow (L/min) 	X	X	X	X	X	X
Weight 	X					
HbA1c	X					
Pharyngeal viral sample 	X	X	X	X	X	X
12-lead ECG 	Х			X		
Chest X-ray 	X					
Serum chemistry	X		X	X		
Hematology (CBC with differential)	X		X	X		
D-dimer, cardiac troponin, CRP, LDH, ferritin 	X		X	X		
Urinalysis	Х					
Serum pregnancy test 	X					

#### Table 1:Study Procedures and Assessments

 daily assessments whilst patient is hospitalized; vital signs = temperature, blood pressure, pulse rate, respiratory rate and oxygen saturation by pulse oximeter and recording of supplemental oxygen requirement as oxygen flow (L/min)  record weight if patient is ambulatory

 pharyngeal samples for SARS-CoV-2 PCR are collected daily, per standard of care. For patients having nasopharyngeal swabs, the same nostril must be used during the study

 for patients on concomitant hydroxychloroquine, the 12-lead ECG will be repeated after 3 hours (±30mins) of initial dose, on Day 2 and Day 4

 Chest X-ray, lab draws will be at the discretion of the Investigator depending on patient clinical condition

 CRP=C-reactive protein, LDH=lactate dehydrogenase

 women of childbearing potential; serum pregnancy test must be negative within 3 days prior to randomization.

#### **3.2 Study Endpoints**

#### 3.2.1 Primary efficacy endpoint

The primary efficacy objective of the study is to evaluate the effect of Opaganib on total supplemental oxygen requirement (area under the curve) using daily oxygen flow (L/min) measurements for 14 days (Day 1 to Day 14).

The primary efficacy endpoint will calculate for each patient the area under the curve of the supplemental oxygen requirement through day 14, using the trapezoidal rule after subtracting the baseline oxygen requirement at each day.

The following rules will be applied:

- If several values of oxygen requirement (L/min) are recorded in a certain day, then for the primary analysis the highest of these values will be taken.
- Days where no supplementary oxygen was needed, will be recorded as 0.
- Subjects who require intubation and mechanical ventilation, at these days will be assigned the maximal supplemental oxygen flow requirement of 8L/min (or if higher, the maximal value observed in the study).
- For subjects discharged from hospital without requiring supplemental oxygen prior to Day 14, the oxygen requirement (L/min) will be assigned thereafter as 0 for each day to Day 14 (in the rare case that subject will re-hospitalize before Day 14, the new supplemental oxygen data will be collected and used, until day 14).
- For the primary analysis, if a patient dies any time before Day 14), all his/her values (D1-D14) will be assigned at the maximal supplemental oxygen flow requirement of 8L/min, or if higher, the maximal value observed in the study.

For patients discharged from hospital with supplemental oxygen prior to Day 14, or early terminate the treatment before Day 14 while still requiring supplemental oxygen, data on the supplemental oxygen up to Day 14 is expected to be collected. However, in the rare case that all supplemental oxygen values are missing after discharge/treatment discontinuation, the individual AUC will be calculated where the last value is carried forward - until Day 14, or death, if occurred before (note, death event is analyzed as specified above). This approach will be employed also if a patient initiates new investigational therapy for COVID-19 within 14 days, in which case the primary analysis will include only measurement taken under study treatment while the rest of the days will be imputed as noted above. Sensitivity analysis will address this scenario as well. To note, according to blinded data review prior to database lock, no cases of such prohibited investigational therapy was recorded.

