#### **3.2.2** Secondary Efficacy Endpoints

The secondary efficacy endpoints are as follows:

1. Time to 50% reduction from baseline in supplemental oxygen based on oxygen flow in L/min

This endpoint will be based on the oxygen flow values used for the primary efficacy endpoint. It will be calculated as the number of days from baseline (Day 1) of study

Statistical Analysis Plan	RedHill Biopharma
Version: 3, Date: 13-DEC-2020	Study ABC-110

medication until the first day when the subject reached a value, which is at least 50% lower than the baseline value (the event of interest). Patients who early terminate the study before reaching this reduction will have their time censored at the last valid observation time point. Patients who will die within the followup timeframe will be censored at the time of the end of the follow-up period, thus taking the highly unfavorable possible outcome for this endpoint. The time frame for this endpoint is from Day 1 until end of off-study-drug followup. Additional analysis will be performed in the time frame of the 14-day-treatment DB Phase period (sensitivity analysis).

To note, in order to focus this endpoint on sustained success, it implies increase in supplemental oxygen negating initial success would be followed for re-achievement of success. Further note, a patient who reached success but did not have any further data supporting this success (i.e. discharged from hospital still requiring oxygen and no further data supporting success afterwards), may be subject to sensitivity analysis where regarded censored at last evaluable time.

2. The percentage of patients no longer receiving supplemental oxygen for at least 24 hours by Day 14

This endpoint will be defined per subject as a binary ("Success" / "Failure") variable with "Success" indicating that a subject no longer receiving supplemental oxygen for at least 24 hours by Day 14, and "Failure" otherwise. Patients who will die within 14-days will be regarded as "Failure", corresponding to the highly unfavorable possible outcome.

To note, in order to focus this endpoint on sustained success, it implies need in supplemental oxygen negating initial success would be followed for re-achievement of success.

3. The time to two consecutive negative swabs for SARS-CoV-2 by PCR, at least 24 hours apart

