# 3.4 Randomization and Blinding

A total of 40 subjects 18 to 80 years old, inclusive will be randomized, using a 1:1 assignment ratio, to treatment with either Opaganib 500 mg Q12 hour (20 subjects) or Placebo (20 subjects), respectively.

A dynamic randomization using the minimization method will be used in this study by Bioforum's DM vendor. Three stratification factors will be used for the minimization algorithm:

- 1. Age at screening,  $\geq 70$  years of age, (yes or no)
- 2. HbA1c at screening,  $\geq 6.5$ , (yes or no);
- 3. Oxygen requirement at baseline, requiring non-invasive positive pressure ventilation (e.g. via PEEP, BIPAP, CPAP, HFNC), (yes or no)

The minimization algorithm will be programmed by Bioforum Ltd using Viedoc system and will employ the Pocock and Simon (Pocock S.J. and Simon R. 1975) methodology with biased coin probability of 0.8 and 'Range' as the variation method. All stratification factors will use the same weight of importance. If the subject meets the eligibility criteria, he or she will be allocated to Opaganib 500 mg Q12 hour or Placebo at 1:1 ratio respectively. Once the enrollment of the subject is approved, the investigator will assign the subject an ID number (subject number) provided by the Viedoc system after running the algorithm on the subject's stratification information.

Treatment assignments will remain blinded to the patient, investigator and hospital staff, as well as the sponsor.

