### 5.6 Subgroups

The subgroup of low-flow vs. high-flow oxygen will be define based on the baseline oxygen required type. Subject will be classified with 'High-Flow' if baseline oxygen

required was positive pressure or high flow nasal cannulas and 'Low-Flow' if baseline oxygen required was regular.

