### 10 SUMMARY OF CHANGES FROM LAST SAP VERSION AND PROTOCOL SPECIFIED ANALYSES

Version 2 of the SAP incorporates edits to the previous version of the SAP and some deviations in text from the latest version of the Clinical Study Protocol.

These edits/deviations, however, were made in response to the FDA recommendations, and attempts to insert greater detail and provide further clarifications. The most significant changes made to the text in this document are summarized in the table below:

Торіс	Change description and rationale	
Analysis	Per-protocol population was defined to address major protocol	
Populations	deviations that may occur, mainly relating to inclusion/exclusion criteria	
Primary efficacy	In Section 3.2.1: Originally, it was thought that multiple units will be used for reporting oxygen flow, and thus a placeholder for algorithm to	
endpoint and	address that was given. Yet, it was confirmed that all oxygen flow values	
analysis	will be reported using the same, L/min unit, therefore referral for further	
	addendum is no longer needed.	
	Imputation rules have been edited as follows:	
	
 
Following FDA recommendation, any death during study will be imputed using maximal supplemental oxygen flow requirement of 8L/min from Day 1 to Day 14 for the primary efficacy endpoint.
 
In case that higher values than 8L/min will be recorded, the SAP now define that 8L/min or if higher, the maximal value observed in the study will be used.
 
The SAP now address the scenario that a patient initiates new investigational therapy for COVID-19 within 14 days, in which case the primary analysis will include only measurement taken under study treatment and the rest of the days will be imputed according to imputation rules.
 
	
	In the sensitivity analysis (section 7.2.1.1): it was clarified that Change	
	from baseline will be analyzed in the model.	
	A supportive per-protocol analysis was added.	
Secondary	Following FDA recommendation and in accordance with the newly	
Efficacy	released COVID-19 guidance to address death as the highly unfavorable	
Endpoints	possible outcome for efficacy endpoints, the secondary endpoints and	
#1,#2,#5	associated analyses have been updated accordingly.	

 Table 2: Summary of changes in Version 2

Торіс	Change description and rationale
Secondary	The endpoint was changed based on FDA recommendation, and analysis
Efficacy	was subsequently fitted to analyze the resulting time to event endpoint.
endpoint #4	

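### Recorded L/min is scored as one scale across devices, so a move from high-flow cannula to BiPAP/CPAP at a lower recorded flow counts as improvement (SAP 3.2.1; SAP 3.2.2 endpoint 1)

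*SAP*

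**What the plan says.** - **Primary endpoint (SAP 3.2.1).** Each patient's daily flow is turned into an AUC "using the trapezoidal rule after subtracting the baseline oxygen requirement at each day". If a day has several values, "then for the primary analysis the highest of these values will be taken". No term for device, inspired oxygen fraction or conversion appears.
- **Worst-value rules (SAP 3.2.1).** There are two. For invasive ventilation: "Subjects who require intubation and mechanical ventilation, at these days will be assigned the maximal supplemental oxygen flow requirement of 8L/min", or the highest value observed in the study if that is larger. For death before Day 14, the same maximum is assigned to all days. Non-invasive positive pressure is not named.
- **Endpoint 1 (SAP 3.2.2).** It reuses the primary endpoint's flow values. Time runs from Day 1 of study "medication until the first day when the subject reached a value, which is at least 50% lower than the baseline value". The note on sustained success withdraws a success only when supplemental oxygen later rises.
- **Units (SAP 10, Version 2 changes).** A placeholder for handling several reporting units was removed because all flow values "will be reported using the same, L/min unit".
- **Devices in the trial.** The third minimization factor in SAP 3.4 is a baseline oxygen requirement "requiring non-invasive positive pressure ventilation (e.g. via PEEP, BIPAP, CPAP, HFNC), (yes or no". In SAP 5.6 a patient is 'High-Flow' if the baseline oxygen "required was positive pressure or high flow nasal cannulas and 'Low-Flow' if baseline oxygen required was regular". Regular oxygen, HFNC and positive pressure are therefore all expected at baseline.

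**The concern.** A shared unit is not a shared scale. A flow in L/min on a nasal cannula, on HFNC and on BiPAP/CPAP need not describe the same amount of support. The SAP protects the score against this only once the patient is intubated or dies. A patient on HFNC at baseline who is moved to BiPAP/CPAP keeps whatever flow is written down. If it is lower, the AUC goes negative, which is the favourable direction, and endpoint 1 may record a success on the day support was stepped up. A step down from BiPAP/CPAP to HFNC can go wrong the other way and score as a worsening.

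What is at stake is the direction of individual scores in the primary endpoint and in the first secondary endpoint, which share the same daily values. SAP 5.3 says the results will be read by the overall pattern of benefit, so an error common to both endpoints would look like agreement between them.

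**Working it through.** **No figure to reproduce.** SAP 3.3 gives 20 patients per arm without a statistical basis, and states no SD or effect size.

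**Inputs from the documents.** Fourteen daily values, trapezoidal rule, change from baseline, highest value of the day (SAP 3.2.1); event when flow is at least 50% below baseline (SAP 3.2.2); 20 per arm (SAP 3.3).

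**Assumptions, not in the documents.** HFNC flow b of 20 to 60 L/min; flow f recorded on BiPAP/CPAP of 5 to 30 L/min. The patient is on HFNC on Days 1-3 and on BiPAP/CPAP on Days 4-14. The highest-of-day rule only delays the change to the first full day on the new device.

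**Formula.** The change from baseline is 0 on Days 1-3 and (f - b) on Days 4-14. The Day 3-4 interval contributes half of (f - b), and the ten intervals from Day 4 to Day 14 contribute (f - b) each:

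AUC = 0.5(f - b) + 10(f - b) = 10.5(f - b)

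A 50% event is scored if f <= 0.5b. The shift in a 20-patient arm mean, compared with the same patient staying at b, is AUC / 20.

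| b (HFNC) | f (BiPAP/CPAP) | AUC, L/min x days | 50% event | Shift in arm mean |
|---|---|---|---|---|
| 20 | 30 | +105 | no | +5.25 |
| 20 | 20 | 0 | no | 0 |
| 20 | 15 | -52.5 | no | -2.6 |
| 20 | 10 | -105 | Day 4 | -5.25 |
| 40 | 30 | -105 | no | -5.25 |
| 30 | 15 | -157.5 | Day 4 | -7.9 |
| 40 | 15 | -262.5 | Day 4 | -13.1 |
| 60 | 15 | -472.5 | Day 4 | -23.6 |

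The extreme corner of the assumed grid, 60 to 5, gives 10.5 x (-55) = -577.5, a shift of -28.9.

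**Reverse move.** BiPAP/CPAP at 10 to HFNC at 40 on Day 4 scores 10.5 x 30 = +315, a worsening.

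**Later intubation.** HFNC 40 on Days 1-3, BiPAP/CPAP 15 on Days 4-9, intubated on Days 10-14 and assigned an assumed study maximum of 60: -12.5 - (5 x 25) - 2.5 + (4 x 20) = -60. The net score is still favourable. The intubation does withdraw the endpoint 1 success, because the assigned flow rises.

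**Do the planned analyses correct the direction?**
- The Hodges-Lehmann and Wilcoxon analyses (SAP 7.2) and the ranked analysis (SAP 7.2.1.4) cap the size, but the patient still ranks among the better outcomes.
- The repeated-measures model (SAP 7.2.1.1) uses the same daily change in flow.
- The covariate adjustment (SAP 7.2.1.2) and the subgroup (SAP 5.6 and 7.5) use baseline information only. The subgroup puts HFNC and positive pressure in one class, so it cannot see a move between them.

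**The case against.** The strongest counter-argument is that both direction and size come from outside the documents. Nothing in either document ranks BiPAP/CPAP above HFNC. SAP 3.4 lists HFNC as an example of non-invasive positive pressure, and SAP 5.6 pools the two; Protocol 17.2 and SAP 6.3 omit HFNC from the factor but give no ordering. How sites recorded flow on positive pressure depends on the case report forms, which SAP 1 lists as reviewed but which are not available here. If the recorded flow is equal or higher, the problem disappears, as the first two rows of the table show. All of this stands, and it is why the point is conditional.

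The plan also limits and exposes the effect. It has the rank-based analyses, the subgroup (which confines a patient on HFNC at baseline to the High-Flow class), individual AUC and profile plots, and a flow and AUC listing (SAP 12). A patient at 4 L/min moved to BiPAP/CPAP at 5 to 15 still scores as worse. Endpoints 2, 5, 6 and 8 do not depend on comparing flows. These points stand as limits on size; none re-scores the affected days.

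A reader might infer more than the documents support:
- **That one such patient outweighs many low-flow recoveries because of the device switch.** A patient going from 4 to 0 on Day 4 scores 10.5 x (-4) = -42, far less than -472.5. But a genuine recovery from 60 to 0 scores 10.5 x (-60) = -630. Much of the contrast is baseline scale, which any absolute AUC carries.
- **That the sign of the treatment difference would change.** With no group difference or SD in the documents, this cannot be computed.
- **That Version 2 removed a method for harmonising devices.** It removed only a placeholder for multiple reporting units.
- **That the rule favours opaganib.** It is the same in both blinded arms, and the error falls in whichever arm the switch occurs.

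**Conclusion.** The point holds as a conditional one. The SAP has no rule for days on non-invasive positive pressure, so a patient on HFNC at baseline who moves to BiPAP/CPAP at a lower recorded flow is scored as improved, and as a 50% reduction at half of baseline or less. In the tabulated cases the AUC runs from +105 to -472.5 L/min x days, or about +5 to -24 in a 20-patient arm mean. This rests on assumed device flows, on a Day 4 switch lasting to Day 14, and on the clinical view that positive pressure is more support than HFNC. How often it would occur is unknown.

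The study tests no formal hypothesis (SAP 5.3), so the effect is on estimated means, the hazard ratio and their intervals, not on an error rate. This should be fixed, but it does not invalidate the primary endpoint or justify replacing it.

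**What to change.** Before unblinding:

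1. **SAP 3.2.2, endpoint 1.** State that a day on a higher support level than at baseline cannot count as the 50% reduction. The proposed order for scoring is regular oxygen < HFNC < positive pressure < intubated, to be confirmed by the sponsor's clinicians.
2. **SAP 7.2.1.** Add one device-aware sensitivity analysis of the AUC. After a step-up, each positive-pressure day takes the higher of the recorded flow and the last flow before the switch; this ends when the patient leaves positive pressure. On a step down from positive pressure to HFNC, the step-down day is not scored as a worsening, and later changes on HFNC are counted from that day.

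Keep the pre-specified L/min score as primary.

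**Effect on the examples.** The 40 to 15 patient moves from -262.5 with an event to 0 without one, a change of 13.1 in the arm mean. The 20 to 30 patient stays at +105. The patient later intubated moves from -60 to (0.5 x 20) + (4 x 20) = +90.

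**Cost.** SAP wording, one extra derivation and one extra table. Some days carry an assigned rather than a recorded flow, which is why this belongs in a sensitivity analysis. The daily device is needed. The documents show its use only at baseline, so if the eCRF does not capture it daily, it must be taken from the chart. The change alters scoring only, not patient care.

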# 17.3 Analysis of the primary efficacy endpoint

The primary efficacy objective of the study is to evaluate the effect of Opaganib on total supplemental oxygen requirement (area under the curve) using daily oxygen flow (L/min) measurements for 14 days (Day 1 to Day 14). The primary efficacy endpoint will calculate for each patient the area under the curve of the supplemental oxygen requirement through day 14, using the trapezoidal rule after subtracting the baseline oxygen requirement at each day. Days where no supplementary oxygen was needed, will be recorded as 0. If several values of oxygen requirement (L/min) are recorded in a certain day, for the primary analysis the highest of these values will be taken. In the primary analysis, for patients who die before Day 14, or require intubation and mechanical ventilation, missing values will be assigned the maximal supplemental oxygen flow requirement of 8L/min. For patients discharged from hospital on supplemental oxygen prior to Day 14, if no values are collected by the site after discharge, the oxygen requirement (L/min) on the day of discharge will be assigned thereafter for each day to Day 14.

The primary analysis will be based on the modified Intent to treat population (mITT), which consist of all patients that were randomized and treated with at least one dose of study drug,

Descriptive statistics of the baseline-adjusted AUC will be presented by group along with 95% confidence interval for the difference in means between the groups.

It is planned to collect supplemental oxygen requirement up to Day 14 even if a patient discontinues treatment prior to Day 14 but continues in the study to Day 14. Further, it is assumed that loss to follow up such that vital status up to Day 14 will be missing is unlikely. Therefore, the primary

analysis will assume that in case that all supplemental oxygen values are missing after treatment discontinuation, the individual AUC will be calculated where the last value is carried forward - until Day 14, or death, if occurred before. A sensitivity analysis to the above missing data handling approach will be performed using an AUC summary statistics approach, in which groups AUC is calculated from the estimated parameters of a Repeated-Measures model.

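### SAP 3.2.1 scores 0 L/min to Day 14 after an off-oxygen discharge without requiring the value to be missing, so a flow recorded at home without readmission would be overwritten

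*SAP*

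**What the plan says.** The primary endpoint is each patient's area under daily oxygen flow from Day 1 to Day 14, computed "using the trapezoidal rule after subtracting the baseline oxygen requirement at each day" (SAP 3.2.1). Among the derivation rules, a patient discharged off oxygen before Day 14 is handled as follows: "the oxygen requirement (L/min) will be assigned thereafter as 0 for each day to Day 14". One exception is given in brackets: "in the rare case that subject will re-hospitalize before Day 14, the new supplemental oxygen data will be collected and used, until day 14".

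Patients discharged while still on oxygen get a different rule. The SAP expects their data to Day 14 to be collected, and carries the last value forward only "in the rare case that all supplemental oxygen values are missing after discharge/treatment discontinuation". Protocol 17.3 is similar for this group: "if no values are collected by the site after discharge, the oxygen requirement (L/min) on the day of discharge will be assigned thereafter".

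Protocol 17.3 has no zero-fill after discharge. Its zero rule is "Days where no supplementary oxygen was needed, will be recorded as 0", which depends on need rather than on discharge status. It also says: "It is planned to collect supplemental oxygen requirement up to Day 14 even if a patient discontinues treatment prior to Day 14". The SAP preface states that the SAP prevails where the two documents differ.

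Secondary endpoint 1 (time to 50% reduction) is built on the flow values used for the primary endpoint. Endpoints 1 and 2 each carry a note on sustained success. For endpoint 2 it reads "it implies need in supplemental oxygen negating initial success would be followed for re-achievement of success".

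**The concern.** The zero-fill is worded as an unconditional assignment. Because re-hospitalisation is the one situation in which new data are to be used, a programmer following the text would not use a flow recorded anywhere else.

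Such values can exist. The oxygen-flow row of Table 1 is marked at Day 7 and Day 14, and Protocol 11.1.3 requires supportive therapy to be recorded until the final follow-up visit. A patient who goes home off oxygen, restarts it there and is not readmitted could therefore have a non-zero flow on file at Day 14 and still be scored as fully weaned.

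The consequence is that an observed relapse receives the lowest possible flow in the primary AUC. The same replacement feeds endpoint 1, where it works against the note that Version 3 of the SAP added so that later loss of success would count. Two patients with the same recorded flow at Day 14 would also be scored differently according to whether they left hospital on or off oxygen.

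**Working it through.** The plan states no figure that can be reproduced here. There is no effect size, SD or power behind the 40 patients, and no expected rate of home relapse. The check applies the SAP's own formula to an assumed patient.

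**Inputs from the documents**
- Trapezoidal AUC of (flow − baseline), Days 1 to 14 (SAP 3.2.1).
- 20 patients per arm (SAP 3.3).
- Daily recording only while in hospital; oxygen flow also marked at Day 7 and Day 14 (SAP Table 1 and its footnote 1).
- Endpoint 1 event: a value at least 50% below baseline (SAP 3.2.2).

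**Assumed patient**
- Baseline 4 L/min; Days 1–5 at 4, 3, 2, 1, 0; discharged off oxygen on Day 5.
- Still off oxygen on Days 6 and 7; on 2 L/min at home on Days 8–14; not readmitted.

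**Formula.** With daily steps, AUC = sum of the 14 differences − half the first − half the last.

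1. Rule as written (0 on Days 6–14). The differences are 0, −1, −2, −3, −4, then nine of −4. Sum = −10 − 36 = −46. AUC = −46 − 0 + 2 = **−44**.
2. Only the scheduled visit values recorded (Day 7 = 0, Day 14 = 2), recorded values used and other days 0. Sum = −10 + 8 × (−4) − 2 = −44. AUC = −44 − 0 + 1 = **−43**. The error of the written rule is **1.0** L/min-day, and 1.0/20 = **0.05** in the arm mean.
3. Home flow recorded every day from Day 8. Sum = −10 + 2 × (−4) + 7 × (−2) = −32. AUC = −32 − 0 + 1 = **−31**. The error is **13**, and 13/20 = **0.65** in the arm mean.

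**General form.** Baseline cancels, so the error is the home flow times the sum of the weights of the overwritten days (1 for an interior day, 0.5 for Day 14). Step 2 is 2 × 0.5 = 1.0. Step 3 is 2 × (6 + 0.5) = 13. If a relapse at 2 L/min were already present at the Day 7 visit and recorded only at Days 7 and 14, the error would be 2 × (1 + 0.5) = 3.0, or 0.15 in the arm mean.

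**Endpoint 1.** Half of baseline is 2 L/min, so a home flow of 2 still meets the 50% criterion and no success is lost. The overwriting matters for this endpoint only when home flow exceeds 50% of baseline.

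**Endpoint 2.** The SAP links only endpoint 1 to the primary endpoint's values. One affected patient would be 1/20 = 5 percentage points of an arm, but only if endpoint 2 is derived from the zero-filled series.

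**The case against.** The best defence is that the rule is a missing-data rule in all but name. SAP 5.4 refers to 3.2.1 for the handling of missing primary-endpoint data, the protocol uses the same verb when filling missing values, and the first rule of 3.2.1 keeps the highest value recorded on a day. On that reading only uncollected days receive 0. The reading is reasonable, but the text does not say so, and a single named exception points the other way. Protocol 17.3 cannot settle it, because the SAP prevails.

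The defence is stronger on size. Daily recording stops at discharge, so for this group the scheduled values at risk are those at Day 7 and Day 14. A reader might take 13 L/min-days as the error from overwriting recorded data, but that needs daily home readings that the plan does not schedule.

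Three further inferences are tempting and not supported:
- *That the error always favours the arm with more early off-oxygen discharges.* It depends on home relapses without readmission, not on the number of discharges.
- *That it cannot be detected.* SAP 8.6 lists all oxygen evaluations, and Listing 16.2.9 shows oxygen requirement with AUC. The overwriting is visible there, though not in the AUC itself.
- *That endpoint 2 is necessarily distorted.* Its own note counts renewed need for oxygen against success.

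The repeated-measures sensitivity analysis (SAP 7.2.1.1) uses observed daily values and so may retain a recorded home flow. It does not say whether assigned zeros count as observed, so it gives no firm protection. Finally, the trial plans no formal inference, which lowers the stakes but does not justify replacing an observation with the most favourable value.

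**Conclusion.** The point stands as a defect in the wording of a derivation rule, and it should be corrected. Read literally, SAP 3.2.1 replaces a recorded non-zero flow with 0 for a patient discharged off oxygen and not readmitted. This is inconsistent with the treatment of patients discharged on oxygen and with the SAP's own sustained-success notes.

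The likely effect is small. On the data the plan schedules, the assumed patient at 2 L/min contributes an error of 1.0 L/min-day; the larger figure of 13 applies only to daily home recording from Day 8. Both scale with the home flow and with the number of such patients, which the documents do not give and which is probably low. Each error lowers the AUC, so the net effect favours whichever arm has more home relapses without readmission. That arm cannot be identified in advance.

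**What to change.** Reword the rule in SAP 3.2.1 along these lines: *For subjects discharged without supplemental oxygen before Day 14, post-discharge days with no recorded value are set to 0; any recorded post-discharge flow, from any setting, is used.* Add a sentence stating whether endpoint 2 is derived from these values.

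Carrying a recorded non-zero home flow forward to the next recorded value can be offered as a sensitivity analysis. It is a choice rather than a necessity, since a single reading carried forward may overstate oxygen use.

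The cost is a sentence or two and minor programming, with no new data collection. A few patients may score slightly less favourably than under the present wording.
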